9.7 Procedural Characteristics

Procedure characteristics will be summarized using continuous and categorical summary statistics and will include information regarding:

- Pre-procedure percent diameter stenosis (%)
- FFR
- Pre-procedure translesional peak pressure gradient (mmHg)
- Stent placement location

A subject listing of the procedure characteristics will also be presented.

9.8 Prior and Concomitant Therapy

All medications (prescription, herbal, and over-the-counter) taken from the time of informed consent through 3 years of follow-up will be recorded in the subject's source records and transcribed into the concomitant medication section of the eCRF.

Subjects are required to receive dual anti-platelet therapy pre-procedure and for a minimum of 3 months post-procedure. The required medications for this study are listed below.

Table 5: Concomitant Medications

Timing	Medication	Procedure
Prior to Procedure	IV Heparin or low molecular weight heparin or bivalirudin	Per routine hospital practice
	Acetylsalicylic acid (ASA)	ASA 325mg loading dose should be given the day of index procedure and prior to placement of the iCAST™ RX Stent System.
	Thienopyridine	The following loading dose of one of the below thienopyridines should be given the day of index procedure and prior to placement of the iCAST™ RX Stent System. Clopidogrel: \geq 300mg Prasugrel: \geq 60mg Ticlopidine: \geq 500mg
During Procedure	IV Heparin or low molecular weight heparin or bivalirudin	Per routine hospital practice
Post Procedure	Acetylsalicylic acid (ASA)	At least 75-325mg per day for a minimum of 3 months
	Thienopyridine	The following maintenance dose of one of the below thienopyridines should be given for a minimum of 3 months or longer based on local guidelines, except when it is medically necessary to take subjects off therapy. Clopidogrel: \geq 75mg Prasugrel: \geq 10mg Ticlopidine: \geq 250mg (twice per day)

Amendment #1: 15Jul13

Concomitant medications will be coded using World Health Organization Drug (WHO-Drug WD 201506) and summarized to the therapeutic drug class (Anatomical Therapeutic Chemical (ATC) 4 classification) and preferred name (generic drug name).

Prior medications are those that started and stopped before exposure to study procedure; concomitant medications are all medications taken during the study period, including those started before but ongoing at the time of the study procedure. Where a medication start date is partially or fully missing, and it is unclear as to whether the medication is prior or concomitant, it will be assumed that it is concomitant.

Medications will be tabulated using frequencies and percentages. Subjects may have more than 1 medication per ATC text. At each level of subject summarization, a subject will be counted once if he/she reports one or more medications. Percentages will be based on the number of subjects in the ITT analysis population.

In addition, the number and percentage of subjects using antihypertensive concomitant medications will be summarized by pre-defined categories as recorded in the electronic case report form (eCRF) (diuretics, beta blockers/calcium channel blocker and ACE/ARBs) and presented overall and by study visit.

Use of anti-platelets medication from hospital discharge to three months will be described as the percentage of subjects taking anti-platelet medication at the 3-month follow-up visit.

A subject listing will be presented and include at minimum the medication, drug classification, start and stop dates.

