	
Eligible subjects will undergo a two-week Medical Documentation Screening period to confirm resistant hypertension (SBP <math>\geq</math> 155mmHg) while on maximum tolerable doses of <math>\geq</math> three anti-hypertensive medications from at least three classes of drugs, one of which must be a diuretic.
 
There must be documented clinical evidence to support likelihood of angiographic findings <math>> 80\%</math> whether it is Duplex Ultrasound (DUS), Computed Tomography angiogram (CTa), Magnetic Resonance angiogram (MRa) or other medical evidence. After meeting screening and clinical eligibility criteria, subjects will undergo a baseline assessment for angiographic eligibility. After angiographic documentation of a <math>\geq 80\%</math> diameter renal artery stenosis or Fraction Flow Reserve (FFR) <math>< 0.8</math> is confirmed, the subject may be enrolled in the trial by placement of the investigational device.
 
The 9-month visit will include a follow-up DUS of the target renal artery. If the DUS is non-diagnostic due to an imaging quality problem, such as overlying bowel gas or body habitus, a second DUS may be attempted. If the DUS is indicative of <math>\geq 60\%</math> stenosis as determined by the core laboratory, or the second DUS remains non-diagnostic, a contrast angiogram will be used to assess the degree of restenosis of the covered stent(s).
 
Clinical follow-up visits will be required for all enrolled subjects at 30-days, 9-months, 12-months, 24-months, and 36-months. A 6-month and 18-month visit will occur via telephone to collect medication usage and Adverse Events (AEs) only. The 36-month clinic office visit will be required as the final safety visit.

SUBJECT POPULATION	Subjects who are candidates for a renal artery revascularization with $\geq 80\%$ visual stenosis and have resistant hypertension with $\geq 155\text{mmHg}$ while on $\geq 3$ anti-hypertensive medications from at least 3 classes of drugs, one of which must be a diuretic.
NUMBER OF SUBJECTS	Up to 138 subjects will be enrolled in this trial.
ESTIMATED TRIAL DURATION	The trial duration is projected for 60 months.

ESTIMATED SUBJECT DURATION	Each subject is expected to be enrolled and followed for a total of 36 months.

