### **3.0 TRIAL DESIGN AND POPULATION**

This is a prospective, single-arm, multicenter clinical trial that will take place at up to 25 US/OUS sites. Primary endpoints have been determined to show the safety, effectiveness, and clinical outcomes of the iCAST™ RX Stent System. Safety and effectiveness will be evaluated based on the primary patency rate at 9-months on a per lesion basis evaluated against a performance goal of published studies with bare-metal stents. The primary clinical endpoint will assess the improvement in systolic blood pressure at 9-months as compared to baseline systolic blood pressure.

Eligible subjects will undergo a two-week Medical Documentation Screening period to confirm resistant hypertension (SBP  $\geq$  155mmHg) while on maximum tolerable dose of  $\geq$  three anti-hypertensive medications from at least three classes of drugs, one of which must be a diuretic.

There must be documented clinical evidence to support likelihood of angiographic findings  $>$  80% whether it is DUS, CTa, MRa or other medical evidence. After meeting screening and clinical eligibility criteria, subjects will undergo a baseline assessment for angiographic eligibility. After angiographic documentation of a  $\geq$  80% diameter renal artery stenosis or FFR  $<$  0.8 is confirmed the subject may be enrolled in the trial by placement of the investigational device.

The 9-month visit will include a follow-up DUS of the target renal artery. If the DUS is non-diagnostic due to an imaging problem, such as overlying bowel gas or body habitus, a second DUS may be attempted. If the DUS is indicative of  $\geq$  60% stenosis as determined by the core laboratory, or the second DUS remains non-diagnostic, a contrast angiogram will be used to assess the degree of restenosis of the covered stent(s).

Clinical follow-up visits will be required for all enrolled subjects at 30-days, 9-months, 12-months, 24-months and 36-months. A 6-month and 18-month visit will occur via telephone to

collect medication usage and AEs only. The 36-month clinic office visit will be required as the final safety visit.

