#### 4.6 CONCOMITANT MEDICATIONS

All medications (prescription, herbal, and over-the-counter) taken from the time of informed consent through 3 years must be recorded in the subject's source records and transcribed into the concomitant medication section of the eCRF.

Subjects are required to receive dual anti-platelet therapy pre-procedure and for a minimum of 3 months post-procedure. The required medications for this study are listed below.

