## APPENDIX 2: DEFINITIONS

ADVERSE EVENT	Any untoward medical occurrence observed in a patient or a clinical investigational subject. This definition does not imply that there is a relationship between the AE and the device under investigation. An AE can therefore be any unfavorable and unintended sign (including any clinically significant abnormal laboratory finding), symptom, or disease temporally associated with the investigational intervention, whether or not considered related to the investigational intervention. Pre-existing conditions, which worsen during a trial, are to be considered AEs.
DE NOVO LESION	A lesion in a native vessel that has not been previously treated.
DISSECTION	Renal artery dissections are stenotic or occlusive lesions most often observed in hypertensive patients with underlying atherosclerosis or fibromuscular disease. Acute dissections may present spontaneously, as a complication of diagnostic or therapeutic angiography or as an agonal event associated with overwhelming systemic illness. Chronic dissections may produce renovascular hypertension or be entirely asymptomatic.
DISTAL EMBOLIZATION	Free flowing blood clot or thrombus material located in the circulation distal to the treated occlusion.
DUAL ANTI-PLATELET THERAPY	The use of thienopyridines in combination with aspirin therapy.
EMBOLI	Something that blocks the flow of blood in a vessel. It may be a gas bubble, a blood clot, a fat globule, a mass of bacteria, or other foreign body that usually forms elsewhere and travels through the circulatory system until it lodges in the vasculature.

ESTIMATED GLOMERULAR FILTRATION RATE	A measure of kidney function calculated based on the Cockcroft-Gault equation:  Male : $eGFR(\text{mL/min}) = (140 - \text{age}) \times \text{weight}(\text{kg}) / 72 \times S_{Cr}$  Female : $eGFR(\text{mL/min}) = (140 - \text{age}) \times \text{weight}(\text{kg}) \times 0.85 / 72 \times S_{Cr}$  $S_{Cr}$ : Serum creatinine, mg/mL
FIBROMUSCULAR DYSPLASIA	Abnormal cellular development or growth in the walls of one or more arteries in the body; most commonly the renal arteries. As a result of abnormal cell development stenosis may develop in these arteries.

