7.4 Visit Windows

The time schedule described in the protocol for each scheduled activity will be followed as closely as possible. The protocol allowable visit windows in Table 3.1 below will be utilized for analysis purposes. All scheduled visits will be windowed according to the table below.

Table 3.1: Primary Visit Windows

Protocol Visit	Target Day	Protocol allowable window (days)
Screening I (Day -14)	-14	-
Screening II (Day -7)	-7	-
Baseline (Day 0)	0	-
Visit 1 (Day 30)	30	+/- 7 (23 – 44)
Visit 2 (6-Months)	182	+/- 30 (152 – 212)
Visit 3 (9-Months)	273	+/- 30 (243 – 303)
Visit 4 (12-Months)	365	+/- 30 (335 – 395)
Visit 5 (18-Months)	575	+/- 30 (545 – 605)
Visit 6 (24-Months)	730	+/- 60 (670 – 790)
Visit 7 (36-Months)	1095	+/- 60 (1035 – 1155)

If a subject has more than one assessment occurring in the same analysis visit window, the data from the visit closest to the scheduled (target) study day will be used for summaries. If two assessments have the same distance from the scheduled study day, the assessment after the scheduled study day will be used.

If two assessments both occur on the protocol-specified day, and both are valid, then the later one will be summarized. All assessments will be provided in the data listings.

The 9-month primary endpoint analysis will be based on the protocol allowable visit windows. Supportive analysis of the primary efficacy endpoint will be performed using a time to event analysis.

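### SAP 9.8 reports antiplatelet use at a 3-month visit that is not scheduled, and its wording does not separate dual from single-agent use

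*SAP*

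**What the plan says.** The requirement is in Protocol 4.6 and is repeated in SAP 9.8: "Subjects are required to receive dual anti-platelet therapy pre-procedure and for a minimum of 3 months post-procedure". Protocol Appendix 2 defines dual therapy as "The use of thienopyridines in combination with aspirin therapy".

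The planned summary is one sentence in SAP 9.8. It opens by naming the period it covers: "Use of anti-platelets medication from hospital discharge to three months will be described as". The measure it then gives for that period is this: "percentage of subjects taking anti-platelet medication at the 3-month follow-up visit". For medication tabulations in general, the same section says that "a subject will be counted once if he/she reports one or more medications".

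On timing, Protocol 3.0 states: "Clinical follow-up visits will be required for all enrolled subjects at 30-days, 9-months, 12-months, 24-months and 36-months". The Protocol Summary adds: "A 6-month and 18-month visit will occur via telephone to collect medication usage and Adverse Events (AEs) only". SAP 7.4 then says of the analysis data: "All scheduled visits will be windowed according to the table below".

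**The concern.** The sentence has three separate weaknesses.

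- **No such visit.** The summary is tied to a contact that neither document schedules.
- **A point in place of a period.** It claims to describe use over about three months but records status at one moment. A subject who stopped and restarted looks the same as one treated throughout.
- **One agent or two.** The requirement is for two agents together. The sentence refers only to antiplatelet medication and does not say that both must be present.

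This sentence is the only summary in the SAP aimed at the required post-procedure regimen over its three months. If it is programmed literally, the cell is empty. If the programmer substitutes another visit or a private date rule, the reported percentage rests on a definition that nobody wrote down beforehand, and a reader cannot tell which definition was used.

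**Working it through.** The plan gives no figure to reproduce. The check sets the rule against the schedule and the windows, and then against the requirement.

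**Step 1: contacts after the procedure.** Protocol 3.0, Protocol 4.5, Protocol Appendix 4 and SAP Table 2 agree: 30 days, 6 months (telephone), 9 months, 12 months, 18 months (telephone), 24 months and 36 months. None is at 3 months.

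**Step 2: analysis windows.** Inputs from SAP Table 3.1:

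| Contact | Target day | Window |
|---|---|---|
| Day 30 | 30 | 23 to 44 |
| 6 months | 182 | 152 to 212 |

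- Month 3, taken as half of the SAP's 6-month target: 182 / 2 = day 91.
- Distance from the close of the day-30 window: 91 − 44 = 47 days.
- Distance to the opening of the 6-month window: 152 − 91 = 61 days.
- Days in neither window: 45 to 151, which is 151 − 45 + 1 = 107 days.

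Taking month 3 as day 90 gives 46 and 62 days, with the same result. Because scheduled visits are assigned by these windows, none can supply a 3-month value.

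**Step 3: the rule against the requirement.**

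| Feature | Requirement | SAP 9.8 summary |
|---|---|---|
| Agents | Aspirin and a thienopyridine together | Antiplatelet medication, not further defined |
| Time | At least three months after the procedure | Status at one time point |
| Permitted stops | Allowed when medically necessary (Protocol 4.4; thienopyridine row of Protocol Table 2 and SAP Table 5) | Not mentioned |

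On the literal wording, a subject on aspirin alone and a subject on both agents are counted alike.

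**Step 4: other planned outputs.** SAP 9.8 tabulates medications by ATC level 4 class and generic name. That shows aspirin and each thienopyridine separately, but not whether they overlapped or for how long. Presentation by study visit is planned for antihypertensives only. The subject listing carries start and stop dates, but no rule turns them into a three-month dual-therapy status.

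**Step 5: whether the data exist.** Protocol 4.6 has all medications recorded from consent through 3 years, Protocol 8.4 requires start and stop dates in the source notes, and Protocol Appendix 4 collects concomitant medications at day 30 and again at the 6-month call, on either side of month 3. A date-based derivation is therefore feasible.

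**The case against.** The strongest reply is that the fault is a wrong time-point label on a minor descriptive table. The medication record is continuous and dated, so status at month 3 can be recovered. SAP 9.8 states the dual requirement and lists both components a few lines above the summary. Generic-name tables and the listing allow a subject-by-subject check. Enrolment stopped at 68 subjects, and SAP section 2 already treats all inference as descriptive.

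Much of this stands, and it rules out three stronger readings that a reader might infer:

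- *That the data are missing for every subject.* Only a visit-based value is missing; the dated medication record covers the period.
- *That the SAP accepts one agent as compliant.* It sets no compliance measure or threshold and never says that any antiplatelet drug will do. The term is undefined, which is a different fault.
- *That the fault undermines the patency result.* SAP 8.2 plans no covariate adjustment, the patency subgroups in SAP 9.9.4 are laterality, gender and age, and no planned analysis uses antiplatelet status.

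The reply does not rescue the rule itself. The other outputs do not give the combination over the period, and recoverable data still need a stated derivation.

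**Conclusion.** The sentence in SAP 9.8 cannot be run as written. Even with a visit supplied, it would not describe the required three months of dual therapy. The size is small: one descriptive summary of treatment received, with no endpoint, hypothesis test, sample size or error rate affected. How far a single-agent count would exceed a dual-agent count cannot be worked out from the documents.

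The conclusion rests on reading the schedule as complete, which is safe because the protocol and SAP agree, and on taking month 3 as day 90 or 91. Any choice from day 45 to day 151 gives the same answer.

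**What to change.** Replace the visit-based sentence with a derivation from concomitant-medication start and stop dates:

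1. Report the percentage of subjects on aspirin plus a thienopyridine from discharge through a stated study day, for example day 90, and the percentage on each agent separately over the same interval. State what serves as the start if a discharge date is not available.
2. Show medically necessary stops as their own category where the reason is recorded, so that permitted stops are not merged with other stops. The documents do not show that a reason is collected for every stop. Protocol 6.3.4 captures medication interruption or discontinuation as an action taken for an adverse event, which is at best a partial source. Unknown reasons should be shown as such.
3. State the denominator, including how subjects who died or left before the chosen day are counted.
4. Add a rule for partial stop dates. SAP 9.8 covers missing start dates only. SAP 7.3.1 imputes the first of the month for a missing day but is framed around medical history and baseline dates. Carried over to stop dates, it could shorten recorded use by up to 30 days (the 31st moved to the 1st).

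The cost is one derived variable and a few date-handling rules. No new data collection is needed, and no treatment requirement changes.

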9.9 Analysis of Primary Endpoints

Statistical tests relating to the primary endpoints will be one-sided with p-values less than 0.025 deemed significant.

Amendment #1: 15Jul13

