## 5.0 STATISTICAL CONSIDERATIONS AND ANALYSIS PLAN

### 5.1 ASSUMPTION OF PRIMARY ENDPOINT RATE

The endpoints will be tested in a sequential manner:

1) Functional Endpoint

Assessment of primary patency rate at 9-months, defined as continuous patency without the occurrence of a total occlusion of the original lesion, without a re-intervention to treat a partial or total occlusion of the stented segment, or bypass of the stented segment due to clinically-driven restenosis or occlusion.

Followed by:

2) Clinical Endpoint

Improvement in systolic blood pressure (SBP) at 9-months as compared to baseline systolic blood pressure.

If the null hypothesis for the functional goal is rejected at the 0.025 level of significance, the null hypothesis for the clinical goal will be tested at the 0.025 level. If rejected, success will be declared for both Performance Goals. Otherwise, if only the first (primary patency) null hypothesis can be rejected, success will be declared only for that Performance Goal. This sequential approach controls the overall significance level at 0.025. Of note, no success can be declared if the null hypothesis for the primary patency goal was not rejected, regardless of the outcome for the other Performance Goal.

For the primary patency endpoint, the proportion of subjects experiencing this outcome will be compared to the predefined Performance Goal of 0.70. Formally, the hypothesis to be tested is:

$H_0$ : The incidence  $p_{PP}$  of primary patency at 9-months is less than or equal to 0.70.

$H_0$ :  $p_{PP} \leq 0.70$

$H_A$ : The incidence  $p_{PP}$  of primary patency at 9-months is greater than 0.70.

$H_A$ :  $p_{PP} > 0.70$

The derivation of the Performance Goal is described in Section 5.2.1 Derivation of the Performance Goal for Patency.

For the SBP endpoint, the change between SBP from baseline to 9-month follow-up will be compared to a predefined Performance Goal of 10mmHg. Formally, the hypothesis to be tested is:

$H_0$ : The mean difference between SBP at 9-months and baseline,  $\mu_{\Delta\text{SBP}}$ , is less than or equal to 10mmHg.

$$H_0: \mu_{\Delta\text{SBP}} \leq 10\text{mmHg}$$

$H_A$ : The mean difference between SBP at 9-months and baseline,  $\mu_{\Delta\text{SBP}}$ , is greater than 10mmHg.

$$H_A: \mu_{\Delta\text{SBP}} > 10\text{mmHg}$$

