### **5.3.4 MULTIPLICITY ADJUSTMENT**

Alpha for the primary hypotheses will be controlled by testing the endpoints hierarchically. Patency will be tested first followed by systolic blood pressure. The test for systolic blood pressure will only be conducted if the patency Performance Goal is met.

Two additional secondary endpoints will be evaluated hierarchically if and only if the primary objective is met. In order to control alpha, the endpoint of clinically driven TLR will be tested as described below, followed by changes in the number or dosage of anti-hypertensive medications as compared to baseline.

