6.2 Changes from the Analyses Planned in the Protocol/CIP

Due to the early termination of enrollment for Protocol/CIP No. iCAST™ RX-ARAS-001, all inferential analysis should be interpreted as descriptive and will be carried out in an exploratory manner.

The following changes were applied:

1. Missing data will not be imputed.
2. Sensitivity analysis will be limited to evaluating the primary analysis results using the per protocol population.
3. Supportive analysis of the revascularization information using a time to event approach will be performed.

Confidential

7. BASELINE, EFFICACY and SAFETY EVALUATIONS

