8.7 Multiple Comparisons/Multiplicity

Due to early termination of study enrollment, the results from the primary and secondary efficacy analyses will be interpreted descriptively and therefore the analysis will not be adjusted to control the Type I error.

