9.10 Analysis of Secondary Endpoints

Due to study enrollment termination, the secondary endpoints will not be evaluated using a gatekeeping or hierarchical approach. All secondary analyses will be performed using the ITT analysis population and missing data imputation will not be performed.

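### SAP 9.9 still calls primary p-values below 0.025 significant after the SAP made all inference descriptive and dropped the patency-then-SBP gate

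*SAP*

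**What the plan says.** **Protocol.** Section 5.1 tests the two primary endpoints in order, each at one-sided 0.025, and states: "This sequential approach controls the overall significance level at 0.025". It adds that "no success can be declared if the null hypothesis for the primary patency goal was not rejected", whatever the SBP result. Section 5.3.4 repeats the order: "The test for systolic blood pressure will only be conducted if the patency Performance Goal is met". The 0.025 threshold also stands in section 5.3.1, where this sequence governs it.

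**SAP, status of inference.** Sections 2 and 6.2 say that, because enrollment ended early, "all inferential analysis should be interpreted as descriptive and will be carried out in an exploratory manner". Section 8.7 says the primary and secondary efficacy results "will be interpreted descriptively and therefore the analysis will not be adjusted to control the Type I error". Section 9.10 says "the secondary endpoints will not be evaluated using a gatekeeping or hierarchical approach".

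**SAP, primary analysis.** Section 9.9 opens with: "Statistical tests relating to the primary endpoints will be one-sided with p-values less than 0.025 deemed significant". Sections 9.9.1 (patency) and 9.9.2 (SBP) each plan a p-value against the Performance Goal. Neither sets an order, and 9.9.2 puts no condition on the patency result. The hypotheses in SAP 5.7 do not mention a sequence either.

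**The concern.** A threshold below which a result is called significant is a decision rule, and a purely descriptive analysis has none. SAP 9.9 therefore cannot be followed to the letter together with 2, 6.2 and 8.7. The sentence in 9.9 is nearly the one in Protocol 5.3.1, but the sequence that made it safe did not come with it.

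What is at stake is the word used in the report. Section 9.9 governs the primary analyses and carries no caveat, no nominal label and no cross-reference to 8.7. Tables and text written from it could call the SBP reduction significant after patency has missed its goal. The protocol allows no success in that case.

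**Working it through.** **Inputs from the documents.** One-sided alpha 0.025; patency goal 0.70, assumed rate 0.82; SBP goal 10 mmHg, assumed reduction 13.7 mmHg, SD 12 mmHg; 125 evaluable subjects, 10% attrition (Protocol 5.1 and 5.2, SAP 5.5); 68 enrolled (SAP 6.1); a recent trial's 1.2 lesions per patient (Protocol 2.1).

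**Assumptions not in the documents.** 68 evaluable subjects, or 61 after 10% attrition (68 × 0.9 = 61.2); one lesion per subject unless stated; independent tests unless a correlation is given.

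**1. The plan's own figures.**
- Patency, n = 125: P(X ≥ 98 | 0.70) = 0.0230 and P(X ≥ 98 | 0.82) = 0.876. This matches the stated limit of 27 failures and 87% power.
- SBP, n = 125: noncentrality (3.7/12) × √125 = 3.45, power 0.928, critical mean 12.1 mmHg. Stated: 92% and 12 mmHg.
- Joint power: 0.87 × 0.92 = 0.80, as stated.
- Overall alpha: with both nulls true, any false claim in the fixed sequence needs a false patency rejection first, so the familywise error is at most 0.025, as stated.

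**2. The same threshold without the gate (both nulls true).**
- Independent tests at full alpha: 1 − 0.975² = 0.0494. Bound for any dependence: 0.025 + 0.025 = 0.05.
- Simulated correlation of 0.3, 0.5 and 0.8 between the tests: 0.048, 0.045 and 0.039.
- The exact binomial test does not spend its full alpha. At n = 68 it needs at least 56 patent (exact alpha 0.0150): 1 − 0.975 × 0.9850 = 0.040. At n = 61 it needs at least 50 (exact alpha 0.0248): 1 − 0.975 × 0.9752 = 0.049.

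**3. How often SBP would pass while patency fails.**

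| | n = 68 | n = 61 |
|---|---|---|
| Patency power at 0.82 | 0.546 | 0.582 |
| SBP power at 13.7 mmHg, SD 12 | 0.707 | 0.659 |
| SBP passes, patency fails; both at design values | 0.707 × 0.454 = 0.32 | 0.659 × 0.418 = 0.28 |
| SBP passes, patency fails; true patency 0.70 | 0.707 × 0.985 = 0.70 | 0.659 × 0.975 = 0.64 |

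With 68 subjects and 1.2 lesions each (81 lesions, treated as independent), patency power is 0.616. The third-row figure becomes 0.707 × 0.384 = 0.27, and the error in step 2 becomes 0.038.

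The figures in step 3 are not false-positive rates, because SBP truly exceeds its goal in those scenarios. They show how often the report would face the result for which the protocol allows no success.

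**The case against.** The strongest reply is that the SAP already deals with this. Sections 2 and 6.2 cover all inferential analysis, and 8.7 names the primary results. No SAP section contains a rule for declaring success, and the departure from the protocol is disclosed. On that reading, 0.025 in 9.9 is a leftover nominal marker, and familywise error has little meaning where no confirmatory claim is made. Much of this stands: a lone SBP p-value below 0.025 would not be a formal success under this SAP. The reply does not remove the sentence, however, and 9.9 itself carries no such qualification.

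Three stronger readings are tempting, and the documents do not support them.

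- **That SAP 2 and 6.2 themselves abolish the sequence.** They change the status of inference and do not mention the order of tests. Section 9.10 removes gatekeeping by name, but only for the secondary endpoints. For the primary endpoints the loss of the gate is an inference from 8.7 together with the absence of any order in 9.9.1 and 9.9.2.
- **That four ungated tests at 0.025 give 1 − 0.975⁴ = 9.6%.** The rule in 9.9 covers the primary endpoints only. SAP 9.10.1 and 9.10.2 set no significance threshold for TLR or for antihypertensive medication, so no four-test figure follows.
- **That the SAP says the trial supports no inference.** It says inferential analysis will be done in an exploratory way and read descriptively.

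**Conclusion.** The contradiction is in the current SAP text and should be resolved before reporting. Taken literally, 9.9 lets SBP be called significant without patency, and lets at least one false significant primary result occur with probability of about 4 to 5% (bound 5%) instead of 2.5%. The exact value depends on the number of evaluable lesions and on the correlation between the tests, neither of which the documents give.

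The mixed result is not remote: about 0.28 to 0.32 at the design effects with one lesion per subject, and 0.64 to 0.70 if true patency only equals the goal. These rest on 61 to 68 evaluable subjects and independence. The defect affects what the report may say. It does not change any estimate or p-value, and the descriptive label already keeps it short of a licensed confirmatory claim.

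**What to change.** **Preferred, and consistent with SAP 2, 6.2 and 8.7.** In 9.9, delete the clause that deems p-values below 0.025 significant. State that the primary p-values are nominal and descriptive and that no success will be declared. In 9.9.1 and 9.9.2, report each primary estimate with its two-sided 95% confidence interval in place of the one-sided 95% limits. SAP 8.1 already plans two-sided exact 95% intervals for discrete variables and 95% intervals for means, so little programming is added.

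**Alternative.** If the sponsor wants to keep the threshold, 9.9 must restate that SBP is called significant only if patency is met. Section 8.7 must then be aligned, since it disclaims Type I error control, and the descriptive statements in 2 and 6.2 need a matching qualification. This restores the 0.025 bound but takes more than one sentence.

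Neither route needs new data or more subjects.
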